Corneal Biomechanics and Corneal Reshaping Therapy NCT02719535 March 25 2016

(a) Introduction

Myopia is highly prevalent in Asian populations, especially Chinese populations [1], and now affects Americans and Europeans as well.[2-3] Low to moderate myopia is not a major concern, but high myopia (more than 6D) is associated with retinopathy and glaucoma and is an economic burden on society.[4]

Various treatment options have been proposed to reduce the progression of myopia, including the use of pharmaceutical agents and different types of corrective lenses. [5-8] Corneal reshaping, also called orthokeratology, is an intervention with proven efficacy in retarding myopia progression. [10]

In orthokeratology, the corneal curvature is altered after a patient wears the lenses. The effective treatment range is usually not more than 5D of myopia and not more than 1.5D of astigmatism. In addition, orthokeratology can be slow or ineffective in some patients. This may be related to the pre-treatment corneal parameters such as the apical radius and eccentricity.[11] Corneal biomechanical properties may also be a factor, but accurate measurement of the influence is difficult.

Most interventions for myopia control begin in early childhood. After commencement of the treatment, several years of continual monitoring is required to confirm its efficacy. If the intervention is eventually ineffective, then the time would have been wasted. The goal of the proposed study is to investigate whether corneal biomechanics are predictive of successful orthokeratology. If pre-treatment corneal biomechanics combined with other conventional corneal parameters do not indicate successful orthokeratology, patients can be advised to try other more effective interventions earlier.

(b) Objectives

- 1. To monitor the changes of corneal biomechanics from long-term (6 months) successful orthokeratology
- 2. To determine if corneal biomechanics is predictive of the rate of orthokeratology

(c) Methods

Subjects

Young, healthy, myopic adults with no history of long-term contact lens wear and ocular disease were recruited. Subjects who occasionally wear soft lenses (such as for sports) were eligible. The inclusion criteria included myopia between -4.00D and -5.00D sphere, and with-the-rule astigmatism (axis 180 ± 30) of not more than 1.50D, where the spherical equivalent was between -4.00D to -5.75D. The difference in myopia between the two eyes was within 1D for both the sphere and cylinder components. The inclusion criterion in refractive error for this study is to eliminate the confounding factor for orthokeratology caused by a wide refractive range. The best-corrected visual acuity was at least 0.10 logMAR in each eye when measured using the Early Treatment Diabetic Retinopathy Study (ETDRS) charts (Prevision Vision, La Salle, IL) under a normal room lighting condition.

Procedures

The following baseline data were collected: non-cycloplegic manifest refraction, ocular biometry through partial coherence interferometry (Zeiss IOLMaster; Zeiss Humphrey, Dublin, CA), corneal topography (Medmont E300, Medmont Pty Ltd., Vermont, VIC, Australia), corneal thickness through swept-source optical coherence tomography (Casia SS-1000, Tomey, Nagoya, Japan), and corneal biomechanics using an Ocular Response Analyzer (ORA; Reichert Inc., USA).

Five valid axial length measurements were captured using the IOLMaster, and an average reading was generated for analysis. In corneal topography, three images (scores higher than 95) were automatically captured. The mean value of the simulated steepest and flattest keratometry readings was used for analysis. Corneal thickness was measured using a "3D Corneal Map" scan by the swept-source optical coherence tomography. Three automated measurements were obtained for each scan while the subject focused on a central target inside the instrument. In ORA, three acquisitions were obtained each with a waveform score of at least 6.0. Corneal hysteresis (CH), corneal resistance factor (CRF), and corneal-compensated intraocular pressure (IOPcc) were measured.

After all non-contact procedures, the cornea was anesthetized using one drop of 0.4% benoxinate. Intraocular pressure was measured using Goldmann applanation tonometry (GAT) followed by corneal biomechanics by using a corneal indentation device. Two GAT readings were taken and the mean result was used for analysis. The indenter first touched the central cornea. After the pre-load was stabilized (through an audible sound), the indenter moved forwards and backwards at 12mm/s to indent the cornea by 1mm. The indentation was completed in less than 0.25 seconds. The corneal stiffness was read from the device and the tangent modulus was calculated from the corneal radius of curvature and central thickness. Three corneal indentations were obtained, and the average was used for analysis.

Lenses used

After the suitability for wearing corneal reshaping lenses was confirmed through slit-lamp biomicroscopy, subjects were fitted with orthokeratology lenses. The lenses used were reverse geometry lenses (Menicon Z Night contact lens) made of super high gas permeable material (Menicon Z, DK 163 ISO). Lens fitting was based on the manufacturer's instructions (Easy Fit Software, Menicon Co Ltd., Nagoya, Japan) according to ocular information, including corneal topography, non-cycloplegic manifest refraction, and horizontal visible lens diameter. Lens fitting was assessed with fluorescein. An optimal fluorescein pattern consisted of 3 to 4mm of central touch, 1 to 1.5mm of mid-peripheral pooling and 1 to 1.5mm of peripheral alignment. A bull's eye fluorescein pattern was considered an optimum fit.

Wearing schedule

After a successful trial fit, a delivery visit was arranged. The subjects were returned to the clinic after an overnight lens wear. The same fluorescein pattern was maintained after overnight orthokeratology. The subjects were the lenses every night and they were required to return regularly. Further follow-up visits were taken place after the first week, 1 month, 3 months and 6 months of lens wear. Each visit was within two hours after waking up in the morning and the lenses being removed.

In addition to corneal topography, corneal thickness, and corneal biomechanics measurements (using both ORA and corneal indentation device), subjective refraction and ocular biometry were included in all follow-up visits. Both the habitual and best-corrected visual acuities were measured.

Ethics clearance was obtained from the institutional review board of The Hong Kong Polytechnic University. Informed consent was obtained from all participants included in the study. This study was registered at ClinicalTrials.gov (NCT02719535, registered March 25, 2016) and in the University of Hong Kong HKU Clinical Trials Register (HKUCTR-1957, registered Feb 1, 2016).

Analysis of data

The corneal parameters and refractive error obtained in each aftercare visit were compared with the baseline data. Data of one eye of each subject who completed the 6-month orthokeratology were analyzed, with the eye with residual sphere closer to plano at the 6-month visit being selected. If the residual sphere was the same in both eyes, then the eye with less residual astigmatism was selected. For subjects with the same residual refractive errors in both eyes, the right eye was selected. Normality was checked using the Shapiro-Wilks test. Repeated-measure analysis of variance or the Friedman test were used to compare changes in ocular parameters throughout the study, that is, from baseline to the end of the 6-month orthokeratology. Baseline ocular parameters that could best predict myopia reduction were identified through linear regression (Pearson or Spearman). Reduction of sphere at the 6-month visit was used as the dependent outcome response, and the various baseline ocular parameters were treated as independent predictors. All data analysis and graphical presentation were completed using SigmaPlot 13 (Systat Software, Inc.).

(d) References

- 3. Pärssinen O. The increased prevalence of myopia in Finland. Acta Ophthalmol. 2012;90: 497-502.

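### The refractive entry window limits but does not eliminate variation in baseline sphere, which is part of the Objective 2 outcome and is not adjusted for

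*Combined protocol and SAP*

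**What the plan says.** All references are to the combined protocol and SAP, section (c) Methods unless stated.

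- **Subjects.** "The inclusion criteria included myopia between -4.00D and -5.00D sphere". Astigmatism may reach 1.50 D, and "the spherical equivalent was between -4.00D to -5.75D". The stated purpose is: "The inclusion criterion in refractive error for this study is to eliminate the confounding factor for orthokeratology caused by a wide refractive range".
- **Lenses used.** Fitting follows the manufacturer's software, "according to ocular information, including corneal topography, non-cycloplegic manifest refraction, and horizontal visible lens diameter". No target correction is stated.
- **Analysis of data.** "Baseline ocular parameters that could best predict myopia reduction were identified through linear regression (Pearson or Spearman", the bracket closing there. "Reduction of sphere at the 6-month visit was used as the dependent outcome response", and "the various baseline ocular parameters were treated as independent predictors". The predictors are not listed, and no adjusted model is described. One eye per 6-month completer is analysed, "with the eye with residual sphere closer to plano at the 6-month visit being selected".
- **(a) Introduction and (b) Objectives.** The goal is to learn whether pre-treatment biomechanics predict successful treatment. Objective 2 itself speaks of the rate of orthokeratology.

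**The concern.** Restricting entry narrows a confounder but does not remove it. Here the variable left over is more than a possible confounder, because it enters the response by arithmetic.

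Two eyes show the effect. One starts at -4.00 D and ends at plano, a reduction of 4.00 D. The other starts at -5.00 D and ends at -0.75 D, a reduction of 4.25 D. The plan's eye-selection rule favours the eye nearer plano, yet the regression scores the second eye higher.

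Two things are at stake for Objective 2:

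- Spread in baseline sphere adds variance to the outcome that has nothing to do with under-response. A real link with biomechanics becomes harder to see.
- A baseline measure that correlates with baseline sphere can appear to predict response when it only tracks the starting point. Baseline sphere itself is the plainest case, and the wording on predictors does not exclude it.

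**Working it through.** The plan states no SD, sample size or effect size, so there is no figure to reproduce. Everything below except the window is an assumption.

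**1. The window.** Sphere runs from 4.00 to 5.00 D of myopia, a 1.00 D range. The spherical-equivalent limits do not narrow it, since 5.00 + 1.50/2 = 5.75 D is just the extreme that the sphere and cylinder limits already allow.

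**2. The outcome.** Let B be baseline myopia and S signed residual myopia (negative if over-corrected). Reduction is R = B - S. The sign matters: an eye going from -4.00 D to +0.50 D has R = 4.00 - (-0.50) = 4.50 D.

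**3. Share of outcome variance due to baseline.** Let S = a + kB + e, with e independent of B and SD(e) = s. Then R = (1 - k)B - a - e, and

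share = (1 - k)²Var(B) / [(1 - k)²Var(B) + s²].

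Var(B) is 1/12 = 0.0833 (SD 0.29 D) if entry is evenly spread, and 0.125 (SD 0.35 D) for five equally likely 0.25 D steps. Worked case, k = 0, s = 0.25 D: 0.0833/(0.0833 + 0.0625) = 57%, and 0.125/(0.125 + 0.0625) = 67%.

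| s (assumed) | k = 0, even / steps | k = 0.5, even / steps | k = 1 |
|---|---|---|---|
| 0.25 D | 57% / 67% | 25% / 33% | 0% |
| 0.50 D | 25% / 33% | 8% / 11% | 0% |

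Outside that range of s, with k = 0, the share is 13% to 18% at 0.75 D and 8% to 11% at 1.0 D. If entry clusters (SD of B assumed 0.20 D), it is 39% at s = 0.25 D and 14% at 0.50 D. It exceeds one half only if s is below about 0.29 D (even) or 0.35 D (steps).

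Taking the eye nearer plano shrinks the residual SD and so raises the share. In simulation (five steps, k = 0, fellow eye within 0.50 D, between-eye residual correlation 0.5 to 0.8, mean residual 0 to 0.3 D), 67% became 73% to 83%, and 33% became 44% to 54%.

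**4. Dilution.** For a predictor unrelated to B that correlates 0.5 with e, the size of its correlation with R is 0.5 × √(1 - share).

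- k = 0: 0.5 × √(1 - 0.667) = 0.29 to 0.5 × √(1 - 0.25) = 0.43.
- k = 0.5: 0.5 × √(1 - 0.333) = 0.41 to 0.5 × √(1 - 0.077) = 0.48.

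**5. Bias.** For a predictor with correlation c with B and no link to e, the correlation with R is c × √share.

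- c = 0: zero.
- c = 0.3, k = 0: 0.3 × √0.25 = 0.15 to 0.3 × √0.667 = 0.24.

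In simulation (assumed 30 subjects, five steps, k = 0, nominal 5% test), the unadjusted false-positive rate was 5% at c = 0 and 15% to 26% at c = 0.3.

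**6. What adjustment does.** If the fitted model is S = α + βX + γB, then because R = B - S the fitted model for R is -α - βX + (1 - γ)B. The coefficient of X is the same apart from sign, whichever response is used. Residual sphere without the covariate is not a general cure, because S still contains kB.

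**The case against.** The strongest reply has four parts.

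- **The stated purpose is narrower than it first looks.** It concerns confounding from a *wide* range, and the window does prevent that. The plan does not say that the window replaces adjustment. This is fair as a reading of intent. The variation that remains is still unaddressed.
- **The residual may rise with baseline.** The Introduction puts the usual treatment range at up to 5 D, and the entry window reaches that limit. At k = 0.5 the shares roughly halve or fall further, and at k = 1 baseline drops out of reduction altogether. This stands, and it is why a range is given. The proposed covariate covers every value of k.
- **Reduction is a legitimate quantity.** An eye that moved 4.25 D did change more than one that moved 4.00 D, and the documents speak of rate and reduction as well as success. This stands as a point about the estimand. It does not supply the missing adjustment for a plan whose goal is to predict success.
- **Baseline sphere may be among the unlisted predictors.** It may be, but as one more separate Pearson or Spearman predictor it would not adjust the others.

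A reader might also infer that each lens is meant to correct exactly the baseline sphere, so that the analysis predicts the prescription rather than the response. The documents do not support this. Refraction is one input to fitting, no target is given, and nothing shows that the biomechanical measures track baseline sphere inside the window.

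**Conclusion.** The point holds in a limited form. A 1.00 D range of sphere remains, baseline sphere is part of the outcome by arithmetic, and no stated step removes it. With an assumed residual SD of 0.25 to 0.50 D, and before eye selection, its share of outcome variance is about 25% to 67% if the residual is independent of baseline, and about 8% to 33% if the residual rises 0.5 D per dioptre.

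A reader might conclude that the outcome is largely set by baseline sphere. That is not shown: it needs a small residual SD and little dependence on baseline, and the documents give neither. Nor is bias in the biomechanical predictors shown. Without correlation with baseline sphere inside the window, the harm is lost precision only. The change should be made because it is nearly free and settles the matter whichever assumption is true.

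**What to change.** - **Subjects:** replace *eliminate* with *limit*.
- **Analysis of data:** include baseline sphere as a fixed covariate in every Objective 2 regression, with partial correlation where Pearson or Spearman is used. Alternatively, model signed 6-month residual sphere given baseline sphere. The predictor coefficient is the same apart from sign in a linear model. That identity need not hold for ranks, so state in advance which response is used.
- **Reporting:** give each biomechanical measure's correlation with baseline sphere, and do not present baseline sphere itself as a predictor of success.

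The cost is one degree of freedom and a few sentences. Baseline refraction is already collected. Correlations for sphere-related parameters may look weaker than they would unadjusted.

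### The Objective 2 regression is limited to 6-month completers, so anyone who stops earlier is dropped although refraction is planned at 1 week, 1 month and 3 months

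*Combined protocol and SAP*

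**What the plan says.** Section (c) Methods, Analysis of data, defines one analysis set: "Data of one eye of each subject who completed the 6-month orthokeratology were analyzed". The eye is the one whose residual sphere is nearer to plano at 6 months, with ties settled by residual astigmatism and then by taking the right eye. For the prediction analysis, "Reduction of sphere at the 6-month visit was used as the dependent outcome response", with baseline ocular parameters as predictors. The same section uses the interim visits for change over time: "The corneal parameters and refractive error obtained in each aftercare visit were compared with the baseline data". No other analysis set, missing-data method or sensitivity analysis is given.

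Section (c) Methods, Wearing schedule, sets the visits: "Further follow-up visits were taken place after the first week, 1 month, 3 months and 6 months of lens wear". It adds that "subjective refraction and ocular biometry were included in all follow-up visits".

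Section (b) gives two objectives. The first is "To monitor the changes of corneal biomechanics from long-term (6 months) successful orthokeratology". The second is "To determine if corneal biomechanics is predictive of the rate of orthokeratology". The Introduction gives the motive: "orthokeratology can be slow or ineffective in some patients", and early prediction would let such patients turn sooner to another intervention.

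**The concern.** The completer set suits Objective 1, which is worded for successful 6-month wear. It does not suit Objective 2, which carries no such limit and exists to identify slow or poor responders. Poor responders who stay to 6 months are analysed; those who leave are not, and the plan does not ask for them to be counted or described.

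The effect depends on why people stop:

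- If stopping is unrelated to response and predictor, there is no bias, only some loss of precision.
- If poorer responders are likelier to stop, the range of response among completers narrows and the predictor-response association is attenuated.
- If stopping also depends on the baseline predictor, the association can be understated or overstated.

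As written, the plan can neither tell these cases apart nor correct for them, although the interim refractions that would help are already scheduled.

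**Working it through.** **1. Who contributes.** Counting the 1-week to 6-month visits:

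| Last visit attended | Follow-up refractions | Eye rule usable | In change-over-time comparison | In Objective 2 regression |
|---|---|---|---|---|
| 1 week | 1 | no | no | no |
| 1 month | 2 | no | no | no |
| 3 months | 3 | no | no | no |
| 6 months | 4 | yes | yes, all visits | yes, 6-month value only |

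The interim values are used, but only in completers, and they do not enter the prediction regression.

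**2. Assumed inputs.** The documents give no sample size, effect size or dropout rate, so there is no plan figure to reproduce. Everything below is illustrative. Predictor x and 6-month response y are standard normal with true r = 0.40, x being signed so that higher values go with better response. Dropout d is 10%, 20% or 30%.

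**3. Stopping depends on response alone.** The distribution of x given y is then unchanged among completers. With V the completer variance of y (1 if nobody stops),

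completer r = √[ r²V / (1 − r² + r²V) ].

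If exactly the worst responders stop, V = 1 + cλ − λ², with c = Φ⁻¹(d) and λ = φ(c)/(1 − d). At d = 20%: c = −0.8416 and λ = 0.350, so V = 1 − 0.2946 − 0.1225 = 0.583. Completer r = √[0.0933 / (0.84 + 0.0933)] = 0.316.

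For graded stopping, the log-odds of stopping fall by 1 or 1.5 per SD of y, the intercept is solved to give d, and V comes from numerical integration.

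| Stopping on response | V at 10 / 20 / 30% | Completer r |
|---|---|---|
| Random | 1 / 1 / 1 | 0.40 / 0.40 / 0.40 |
| Graded, slope 1 | 0.930 / 0.888 / 0.860 | 0.388 / 0.380 / 0.375 |
| Graded, slope 1.5 | 0.880 / 0.816 / 0.772 | 0.379 / 0.367 / 0.358 |
| Exactly the worst stop | 0.712 / 0.583 / 0.493 | 0.346 / 0.316 / 0.293 |

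The last row is the extreme when poor response alone drives stopping. It is not an overall bound, as the next step shows.

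**4. Stopping also depends on the predictor.** The response slope is 1.5, with a predictor effect of 0.5 or 1.5 log-odds per SD added.

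| Predictor effect | Completer r at 10 / 20 / 30% |
|---|---|
| 0.5; values linked to poor response raise stopping | 0.35 / 0.32 / 0.29 |
| 0.5; values linked to good response raise stopping | 0.41 / 0.42 / 0.43 |
| 1.5; values linked to poor response raise stopping | 0.31 / 0.25 / 0.21 |
| 1.5; values linked to good response raise stopping | 0.46 / 0.49 / 0.51 |

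**5. What the interim refractions recover.** Let y1 be the 1-month response, with assumed correlation ρ = 0.6 or 0.8 with y, and ρ × 0.40 = 0.24 or 0.32 with x. The likelihood estimate of the 6-month slope is b_x + b_1·a. Here a is the slope of y1 on x in everyone seen at 1 month, and b_x and b_1 come from regressing y on x and y1 in completers. The table gives the slope as a share of the true slope, over 10% to 30% dropout and both values of ρ, with response slope 1.5 and a strong predictor effect of 1.5.

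| Stopping depends on | Completers | Likelihood, all stoppers seen at 1 month | Half of stoppers seen |
|---|---|---|---|
| 1-month response | 0.96 to 0.87 | 1.00 | 0.98 to 0.96 |
| 1-month response and predictor | 0.63 to 1.24 | 1.00 | 0.91 to 1.07 |
| Unseen 6-month response | 0.90 to 0.80 | 0.96 to 0.86 | not tabulated |
| Unseen 6-month response and predictor | 0.52 to 1.28 | 0.66 to 1.20 | not tabulated |

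**6. Small samples.** The following use 20% dropout, one predictor at a time and assumed n = 20, 30, 40. The SD of the estimated slope, as a share of the true slope, was 0.59–0.69, 0.47–0.53 and 0.40–0.44 for the two-visit likelihood estimate. For completers it was 0.61–0.70, 0.48–0.54 and 0.41–0.45. A likelihood fit to all visits (one eye, unstructured covariance, stopping on 1-month response with or without the predictor) moved the mean slope from 0.73–1.17 of the truth in completers to 0.98–1.02, without loss of precision.

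**The case against.** The strongest reply is that the problem depends on facts the documents do not contain. No dropout rate is given, and nothing says that poor responders stop wear. If stopping depends on response alone and is graded, r moves only from 0.40 to between 0.39 and 0.36, which sampling error would swamp at n = 20 to 40. At 20% dropout depending on 1-month response, the root mean square error of the slope (as a share of the true slope) improves only from 0.627 to 0.623 (ρ = 0.6) or 0.633 to 0.600 (ρ = 0.8) at n = 20. A clear gain, such as 0.728 to 0.625, needs a strong predictor effect on stopping, for which the documents offer no reason. All of this stands, and it limits the weight of the point.

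Three further objections concern the remedy.

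- *The two-visit estimator is not the proposed model.* The all-visit fit answers this for one eye with unstructured covariance. A two-eye model was not tested, and a lone subject random effect is a restrictive structure.
- *The plan allows for non-normal data, and sphere reduction may be bounded near full correction.* This is fair. Keeping the planned completer regression, with its rank-based option, as a sensitivity analysis covers it in part.
- *For someone who stopped, a modelled 6-month value is a response under wear that did not continue; stopping for failure could instead count as lack of success.* This is also fair. The target should be stated.

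None of these gives a reason to discard refractions already planned, or to leave those who stop uncounted.

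**Conclusion.** The concern holds. The completer restriction is an explicit rule, and it removes early stoppers from an objective meant to identify poor response. Whether it biases the result, how much and in which direction cannot be known from the documents. Under the assumed r = 0.40 and 10% to 30% dropout, the effect is nil for random stopping and small for graded response-driven stopping (0.39 to 0.36). It is moderate if exactly the worst responders stop (0.35 to 0.29). It can be large in either direction if stopping also depends strongly on the predictor (0.21 to 0.51). This is an improvement the plan should make rather than a fatal flaw, and confidence in its practical importance is medium. Objective 1 is not affected.

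**What to change.** For Objective 2:

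- **Report stopping.** Give the number and reasons by visit, and compare baseline biomechanics between completers and non-completers.
- **Use all follow-up refractions.** Include every subject with a baseline and at least one follow-up refraction in a likelihood-based mixed model of sphere reduction by visit. Include a baseline predictor by visit interaction, fit one baseline parameter at a time, and report the 6-month association as the main result. State that for those who stopped it describes response had wear continued.
- **Choose eyes without the 6-month result.** Use a fixed eye for all, or both eyes with a subject random effect. The fixed eye with unstructured covariance over visits is the simpler form and the one checked above.
- **Keep the planned analysis.** Retain the completer regression as a sensitivity analysis, and the completer set for Objective 1.

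The cost is analysis wording and some extra analysis, possibly in software other than SigmaPlot. No subjects, visits or measurements are added. The model corrects only part of the bias if stopping depends on later response that was never seen, and it cannot recover subjects with no follow-up refraction. With little or no dropout the gain is close to nil, and only the report on stopping is then informative.

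### Only one eye per subject is analysed although the selection rule implies data from both; this is a loss of efficiency of uncertain size, not an error

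*Combined protocol and SAP*

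**What the plan says.** All of this is in (c) Methods unless stated.

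- **Analysis of data, unit of analysis.** "Data of one eye of each subject who completed the 6-month orthokeratology were analyzed". The eye is chosen on its result: "with the eye with residual sphere closer to plano at the 6-month visit being selected". The first tie-break is lower residual astigmatism. The last is: "For subjects with the same residual refractive errors in both eyes, the right eye was selected".
- **Subjects.** Eligibility refers to both eyes: "The difference in myopia between the two eyes was within 1D for both the sphere and cylinder components".
- **Wearing schedule.** Topography, thickness and biomechanics are repeated at follow-up, and "subjective refraction and ocular biometry were included in all follow-up visits". The section does not say whether this means one eye or both.
- **(b) Objectives, Objective 2.** "To determine if corneal biomechanics is predictive of the rate of orthokeratology".
- **Analysis of data, regression.** "Reduction of sphere at the 6-month visit was used as the dependent outcome response", and "the various baseline ocular parameters were treated as independent predictors". Outcome and predictors are both properties of an eye.

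The plan gives no sample size, power, inter-eye correlation or reason for using one eye, and it describes no two-eye analysis.

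**The concern.** The analysed eye is unknown until month 6. For the chosen eye to have baseline biomechanics and a full series of visits, both eyes must have been followed from the start. If so, the fellow eye's data were collected and then left out of every analysis, with no apparent saving in data collection.

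At stake is the width of the intervals for the Objective 2 slopes and, to a lesser degree, for the Objective 1 mean changes. With no sample size stated, fuller use of the data already collected is one of the few ways left to improve precision.

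**Working it through.** **Inputs.** The plan has no figure of its own to reproduce. Let rx be the inter-eye correlation of a baseline predictor, re that of the regression residual, and r that of the change from baseline. None is in the documents; every value below is assumed. Each ratio is information from two eyes relative to one eye per subject; a ratio of 1.30 is worth 30% more subjects.

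**1. Objective 2, independence estimating equations with cluster-robust errors:** 2/(1 + rx·re).

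- rx 0.8, re 0.5: 2/1.40 = 1.43
- rx 0.9, re 0.7: 2/1.63 = 1.23
- rx 0.9, re 0.8: 2/1.72 = 1.16
- rx 0.95, re 0.9: 2/1.855 = 1.08

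**2. Objective 2, generalised least squares (GLS) or mixed model:** 2(1 − rx·re)/(1 − re²).

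- rx 0.8, re 0.5: 1.20/0.75 = 1.60
- rx 0.9, re 0.7: 0.74/0.51 = 1.45
- rx 0.95, re 0.7: 0.67/0.51 = 1.31
- rx 0.8, re 0.1: 1.84/0.99 = 1.86
- rx = re = 0.7: 1.02/0.51 = 2.00

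**3. Where the GLS gain comes from.** The ratio is the sum of a between-subject part, (1 + rx)/(1 + re), and a within-subject part, (1 − rx)/(1 − re). At rx 0.8, re 0.6 this is 1.125 + 0.500 = 1.625, so 0.500 of the 0.625 gain (80%) is the contrast between a person's two eyes. At rx 0.9, re 0.7 it is 1.118 + 0.333 = 1.451. The full gain needs the two slopes to be equal.

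**4. Predictor measurement error.** Assume a true inter-eye correlation of 0.95, reliability 0.8, re 0.6 and a true slope of 0.40.

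- Observed rx = 0.95 × 0.8 = 0.76.
- Information: between 1.76/1.6 = 1.10, within 0.24/0.4 = 0.60, total 1.70.
- Attenuation: between 0.8 × 1.95/1.76 = 0.886; within 0.8 × 0.05/0.24 = 0.167.
- Weighted attenuation: (1.10 × 0.886 + 0.60 × 0.167)/1.70 = 0.632, so the slope is 0.25, against 0.8 × 0.40 = 0.32 for one eye.
- Squared signal-to-noise relative to one eye: (0.632/0.8)² × 1.70 = 1.06.

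A variance ratio of 1.70 thus becomes a useful gain of about 6%. The same steps at reliability 0.9 give about 19%. Simulation with reliability 0.8 to 0.9 gave about 0% to 18%.

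**5. Objective 1, mean change:** 2/(1 + r). At r = 0.5 this is 1.33; at r = 0.8 it is 1.11.

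**6. A trap in the Objective 1 model.** With random intercepts for subject and eye only, both cancel in a change from baseline, so the two eyes' changes are treated as independent. The test statistic is inflated by √(1 + r). A nominal two-sided 5% test then rejects with probability P(|Z| > 1.96/√(1 + r)): 11.0% at r = 0.5 (cut-off 1.600) and 14.4% at r = 0.8 (cut-off 1.461).

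**7. Scale, illustration only.** To detect a correlation of 0.4 with 80% power at two-sided 5%, one eye per subject needs ((1.960 + 0.842)/0.4236)² + 3 = 46.7, that is 47 subjects. A gain of 10%, 30% or 80% would reduce this to 43, 36 or 26.

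**The case against.** The strongest reply is that one eye per subject is a legitimate and simple design choice, and a careless two-eye analysis is worse than none. Both parts stand. A reader might infer that the one-eye analysis is invalid because data are dropped; the documents do not support that, since dropping the fellow eye does prevent correlated eyes from being counted as independent. Step 6 shows that an obvious two-eye model would raise the false-positive rate.

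A second reply is that the gain is speculative. A reader might infer a firm gain of 30% to 80%. That too is unsupported: it rests on correlations that the documents do not give, equal slopes and predictors without error. The within-subject contrast, which carries most of the GLS gain, is the part most exposed to measurement noise.

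Third, bilateral measurement is an inference. The eye comparison makes bilateral month-6 refraction all but certain. For the biomechanics the inference is strong but unstated; the indentation procedure is described for the cornea, without saying one eye or both.

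Fourth, adding less-corrected fellow eyes changes what is described. Objective 1 concerns successful treatment, so this has to be acknowledged.

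Finally, selecting the eye on its 6-month result is a separate and more serious matter. In a simulation with a true standardised slope of 0.40, the better-eye rule returned slopes of about 0.29 to 0.38. That bias is not part of the efficiency argument, although analysing both eyes would remove it too.

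**Conclusion.** The point holds as lost efficiency. The selection rule implies that fellow-eye data exist, and the plan does not use them.

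- **Objective 2 slope:** from about 10% to about 80% or more in equivalent subjects. The low end is independence estimating equations at high correlations, or noisy predictors; particular settings fall lower still (8% in step 1, near zero in some noisy cases in step 4). The high end needs GLS or a mixed model, error-free predictors and equal within- and between-subject slopes.
- **Objective 1 mean change:** about 11% at r = 0.8 to 33% at r = 0.5.

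Every figure is conditional on assumed correlations. What does not depend on them is that the change concerns the analysis only and also ends selection of the eye on its outcome. That makes it worth doing even if the gain in precision proves small.

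**What to change.** In (c) Methods, Analysis of data, replace the one-eye rule and state in Procedures which eyes were treated and measured.

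- **General.** Analyse both eyes of each subject, with the subject as the cluster.
- **Objective 2.** Regress each eye's outcome on that eye's baseline predictor, using generalised estimating equations or a mixed model, with subject-clustered robust errors and a small-sample correction. Include the subject mean of the predictor so that between- and within-subject slopes are reported separately. If they differ, do not pool them; only the between-subject part of the gain then applies to the between-subject slope.
- **Objective 1.** Use a mixed model with visit as fixed effect and random effects for subject, eye within subject, and subject-by-visit. Averaging the two eyes at each visit, or subject-clustered robust errors, would also serve. Random intercepts alone are not enough.
- **Sensitivity analysis.** Keep a one-eye analysis, with the eye fixed without reference to the outcome.

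Cost: no new data, provided both eyes were measured as implied. Software beyond SigmaPlot 13 may be needed. The rank-based route (Friedman, Spearman) needs a clustered counterpart, such as a bootstrap that resamples subjects. The results will describe all treated eyes and not only the better-corrected one, and the report should say so.
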